Cases of drug-induced liver injury (DILI) have been observed with nintedanib treatment in adults. The majority of hepatic events occur within the first three months of treatment, therefore hepatic transaminase and bilirubin levels should be investigated upon the initiation

of treatment with nintedanib, at regular intervals during the first three months of treatment and periodically thereafter or as clinically indicated.

Considering that VEGFR inhibition might potentially be associated with an increased risk of bleeding, patients at known risk for bleeding or who required fibrinolysis, full-dose therapeutic anticoagulation, or high dose antiplatelet therapy have been excluded from participation in the nintedanib trials, and initiation of any of these therapies during the course of the trials required discontinuation of the study medication.

For a more detailed description of the nintedanib profile, please refer to the current IB Nintedanib in Idiopathic Pulmonary Fibrosis, Systemic Sclerosis and Progressive Fibrosing Interstitial Lung Disease [[c01783972-16](#)].

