5.1 PRIMARY ENDPOINT(S)

The primary PK endpoint is the $AUC_{\tau,ss}$ based on sampling at steady state (at week 2 and week 26 visit).

For patients receiving nintedanib in Part A, PK profiles on week 2 and week 26 are planned to be collected. For the primary endpoint $AUC_{\tau,ss}$ the $AUC_{\tau,ss}$ at week 2 will be used. If the week 2 value is missing, then it will be replaced by available $AUC_{\tau,ss}$ at week 26 (or later, if PK visit was postponed). For patients receiving placebo in Part A and nintedanib in Part B, $AUC_{\tau,ss}$ evaluated based on

PK profiles at week 26 (or later, if PK visit was postponed) will be used (which corresponds to week 2 on active treatment).

The primary safety endpoint is the N (%) of patients with treatment-emergent adverse events at week 24, i.e., during the planned double-blind period of the trial.

Thus, the number of patients experiencing at least one adverse event during the double-blind period of the trial will be analyzed, see [Section 7.8](#).

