6. GENERAL ANALYSIS DEFINITIONS

6.1 TREATMENT(S)

For treatment specifications, please refer to CTP Section 4.

The following trial periods will be defined: screening, post-randomization, blinded treatment period (with sub-periods treatment period, off-treatment, residual effect period and follow-up), open-label treatment period (with sub-periods treatment period, off-treatment, residual effect period and follow-up), nintedanib exposure period (with sub-periods treatment period, off-treatment, residual effect period and follow-up), and post-study as follows (Note: As described below, the last day of each of the following periods is excluded from the respective period. It defines the first day of the subsequent period):

- Screening: from informed consent to randomization
- Post-randomization (optional^[a]): from randomization to first randomized trial drug intake in blinded treatment period
- Double-blind period:
 - Blinded treatment period: from first randomized trial drug intake (or re-start of treatment if interruption) to last blinded trial drug intake (or the day before start date of interruption, if interruption) plus one day
 - Blinded off-treatment (optional^[a]): from start date of interruption to re-start of blinded treatment
 - Residual Effect Period: the Residual Effect Period (REP) of nintedanib for the pediatric program is 28 days. This is the period from the last blinded trial drug intake plus one day to last blinded trial drug intake plus 28 days plus one day or the day of first open-label treatment administration (whichever occurs earlier)
 - Blinded follow-up (optional^[a]): from last blinded trial drug intake plus 29 days up to the beginning of post-study period. This period is only created if last blinded trial drug intake took place more than 28 days before trial completion, or for patients having prematurely discontinued the blinded treatment and still continuing the trial
- Nintedanib exposure period:
 - Nintedanib treatment period: from first nintedanib intake (or re-start of treatment if interruption) to last nintedanib intake (or the day before start date of interruption, if interruption) plus one day
 - Nintedanib off-treatment (optional^[a]): from start date of interruption to re-start of nintedanib treatment
 - Nintedanib residual effect period: from the last nintedanib intake plus one day to last nintedanib intake plus 28 days plus one day

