6.7 BASELINE, TIME WINDOWS AND CALCULATED VISITS

As a general rule, the last assessment/measurement observed prior to start of trial medication will be used as baseline. If the time of the assessment/measurement was not captured, and it was on the same day trial medication started, it will be assumed that it was taken prior to the intake of trial medication. For the nintedanib-exposure period, the last measurement prior to the first nintedanib intake was defined as the baseline measurement.

Visit windowing will be performed as described in the following tables, in order to assign data to the relevant study visit based on the actual day of the assessment. Data will be analyzed using the re-calculated visits in the statistical tables. However, in the listings, all visits performed will be displayed (even if outside time-window), along with the re-calculated visit.

Exception:

to account for the short timespan between planned visit 6 (with first open-label intake) and visit 7, a special rule is applied to analyses by visit (not cumulative across visits) in case assignment to visit windows leads to missing values at visit 6 or subsequent visit to take possible multiple measurements in the respective other time window into account.

If such an assessment lies in analysis visit window of visit 7, but not later than 1 month after the planned day of visit 7 and still within the double-blind period, then it is allocated to the analysis visit 6.

Similarly, if such an assessment lies in analysis visit window of visit 6, but after the planned day of visit 6 and not within the double-blind period, then it is allocated to the subsequent visit where this assessment is planned.

If after windowing of visits at baseline, two or more values fall within the same baseline interval, then the last value prior to first drug intake will be taken into account. If after windowing of post-baseline visits, two visits fall in the same interval, then the measurement closest to the planned visit will be taken into account. If only on-treatment values are to be considered, this rule will be applied to on-treatment assessments only. In case two measurements are equidistant from the planned visit, then the last one will be picked.

Table 6.7: 1 Time windowing rules for FVC, SpO₂, missed school days, vital signs (syst. and diast. blood pressure, pulse rate) and laboratory tests (incl. LDH)

Time window of actual day ^[1,2]			Allocated to		

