Start day	End day (included)	Length of the time-window [days]	Visit number	Visit name	Planned day of the visit
-84	1	85	2	Baseline	1
2	29	28	3	2 weeks	15
30	64	35	4	6 weeks	43
65	127	63	5	12 weeks	85
128	176	49	6	24 weeks	169
177	218	42	7	26 weeks	183
219	309	84	8	36 weeks	253
310	407	112	9 (p)	52 weeks	365 (V _p)
(V _p + 1) + (V _{p+1} - V _p)/2	V _{p+1} + (V _{p+2} - V _{p+1})/2	(V _{p+2} - V _p)/2	p+1		V _{p+1} = V _p + 12 x 7
...	Every 12 weeks thereafter	...

V_p denotes the planned day of the visit

^[1] First trial drug intake date is taken into account as reference to calculate time windows

^[2] Only for LDH biomarker analyses: Biomarker values are only considered up to + 7 days after last drug intake.

Table 6.7: 2 Time windowing rules for weight

Time window of actual day ^[1]			Allocated to		
Start day	End day (included)	Length of the time-window [days]	Visit number	Visit name	Planned day of the visit
-84	1	85	2	Baseline	1
2	29	28	3	2 weeks	15
30	64	35	4	6 weeks	43
65	127	63	5	12 weeks	85
128	211	84	6	24 weeks	169
212	309	84	8	36 weeks	253
310	407	112	9 (p)	52 weeks	365 (V _p)
(V _p + 1) + (V _{p+1} - V _p)/2	V _{p+1} + (V _{p+2} - V _{p+1})/2	(V _{p+2} - V _p)/2	p+1		V _{p+1} = V _p + 12 x 7
...	Every 12 weeks thereafter	...

V_p denotes the planned day of the visit

^[1] First trial drug intake date is taken into account as reference to calculate time windows

Table 6.7: 3 Time windowing rules for height and leg length

Time window of actual day ^[1]			Allocated to		
Start day	End day (included)	Length of the time-window [days]	Visit number	Visit name	Planned day of the visit
-84	1	85	2	Baseline	1
2	127	126	5	12 weeks	85
128	211	84	6	24 weeks	169
212	309	98	8	36 weeks	253
310	449	140	9 (p)	52 weeks	365 (V _p)
(V _p + 1) + (V _{p+1} - V _p)/2	V _{p+1} + (V _{p+2} - V _{p+1})/2	(V _{p+2} - V _p)/2	p+1		V _{p+1} = V _p + 24 x 7
...	Every 24 weeks thereafter	...

V_p denotes the planned day of the visit

^[1] First trial drug intake date is taken into account as reference to calculate time windows

Table 6.7: 4 Time windowing rules for dental examination and bone imaging

Time window of actual day ^[1]			Allocated to		
Start day	End day (included)	Length of the time-window [days]	Visit number	Visit name	Planned day of the visit
-84	15	99	2	Baseline ^[2]	1
16	127	112	5	12 weeks	85
128	211	84	6	24 weeks	169
212	309	98	8	36 weeks	253
310	449	140	9	52 weeks	365 (V_p)
450	617	168	11 (p)	76 weeks	533

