As described in Section 7.2.5 of the CTP, laboratory data will be analyzed both quantitatively as well as qualitatively. The latter will be done via comparison of laboratory data to their reference ranges. Values outside the reference range as well as values defined as clinically relevant will be summarized. Treatment groups will be compared descriptively with regard to distribution parameters as well as with regard to frequency and percentage of patients with abnormal values or clinically relevant abnormal values.

Data will be received from a central laboratory, the respective reference ranges will be provided in the ISF.

For INR measurements, no reference range is transmitted by the central laboratory, because the central laboratory does not have information on concomitant medication taken by the subjects, and the reference range for INR depends on whether a subject is taking anticoagulants. The reference ranges for INR will therefore be imputed with 0.8 for the lower limit of normal (LLN) and with 1.2 for the ULN, which correspond to the

reference range defined by the central laboratory for subjects not taking anticoagulants and which is more conservative than the range for subjects taking anticoagulants (LLN=2, ULN=3).

Analyses of laboratory variables will be displayed by treatment and overall for the double-blind period, for the nintedanib exposure period and over the whole trial; please refer to [Table 6.7: 1](#) for time windowing definition.

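### By-visit laboratory tables for the nintedanib exposure period take baseline from first nintedanib but count visits from first trial drug, so placebo switchers' labels overstate time on drug by 24 weeks

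*SAP*

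**What the plan says.** Four provisions of the SAP act together.

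- **Display.** SAP 7.8.2.1: "Analyses of laboratory variables will be displayed by treatment and overall for the double-blind period, for the nintedanib exposure period", and also over the whole trial. For time windows the sentence refers to Table 6.7: 1, whose title includes laboratory tests.
- **Clock.** Footnote 1 of that table: "First trial drug intake date is taken into account as reference to calculate time windows". It makes no exception by analysis period.
- **Use in tables.** SAP 6.7: "Data will be analyzed using the re-calculated visits in the statistical tables". The windowed visit therefore decides the row in which a value appears.
- **Baseline.** SAP 6.7: "For the nintedanib-exposure period, the last measurement prior to the first nintedanib intake was defined as the baseline measurement".

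Under SAP 6.1 the nintedanib exposure period begins at first nintedanib intake. For a child randomised to placebo who completes Part A, that is Visit 6, planned day 169. SAP 6.7 has one windowing exception, for Visits 6 and 7. It moves values between neighbouring trial visits according to whether they fall before or after the open-label start, and it does not restart the count of days.

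**The concern.** The nintedanib exposure period brings together all exposed children, whichever arm they were randomised to. For this period the SAP moves the baseline to the start of nintedanib and leaves the visit clock at the start of trial drug. For a switcher, change from baseline is then measured from one origin and labelled from another.

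Elsewhere the SAP does use time on drug. In SAP 5.1 the week 26 PK profile of a placebo switcher is used as one "which corresponds to week 2 on active treatment". In SAP 5.4.3 the exposure-related time-to-event analyses start from first intake in the period concerned. The laboratory windows look like an omission rather than a choice.

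At stake is whether a reader of a by-visit laboratory table for this period can take the row label as time on nintedanib. Early time on drug has particular interest here. Protocol 1.2 says of adults: "The majority of hepatic events occur within the first three months of treatment".

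**Working it through.** **Inputs**

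- Planned visit days and windows, SAP Table 6.7: 1: 2 weeks, day 15 (2 to 29); 6 weeks, day 43 (30 to 64); 12 weeks, day 85 (65 to 127); 24 weeks, day 169 (128 to 176); 26 weeks, day 183 (177 to 218); 36 weeks, day 253 (219 to 309); 52 weeks, day 365 (310 to 407); then every 12 weeks.
- Planned switch: Visit 6, day 169 (protocol flow chart).
- Planned numbers: about 20 nintedanib and 10 placebo (protocol synopsis).

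**Reproducing the plan's own figures.** Planned day = 7 × weeks + 1. For week 26, 7 × 26 + 1 = 183, as in the table; the other post-baseline planned days agree. For a switcher starting on day 169, nintedanib day = trial day − 168. Visit 7 is then 183 − 168 = 15, that is 2 weeks on drug, which matches SAP 5.1.

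**Planned switcher visits under each clock**

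| Trial day | Label as written | Nintedanib day | Weeks on drug | Window if counted from first nintedanib |
|---|---|---|---|---|
| 183 | 26 weeks | 15 | 2 | 2 weeks |
| 253 | 36 weeks | 85 | 12 | 12 weeks |
| 365 | 52 weeks | 197 | 28 | 26 weeks |
| 449 | 64 weeks | 281 | 40 | 36 weeks |
| 533 | 76 weeks | 365 | 52 | 52 weeks |

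As written, every label is 24 weeks ahead of time on drug (26 − 2, 36 − 12, 52 − 28 and so on). Counted from first nintedanib, the gap is 0, 0, 2, 4 and 0 weeks.

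**What the 26-week row contains.** Trial days 177 to 218 are nintedanib days 9 to 50 for a switcher. For a child randomised to nintedanib they are days 177 to 218 on drug. With planned numbers and no dropout:

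- share of the overall row that is about 2 weeks on drug: 10 / (20 + 10) = 33%;
- mean time on drug in that row: (20 × 26 + 10 × 2) / 30 = 18 weeks.

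**Early rows.** As written, the overall 2- and 12-week rows hold about 20 children. Counted from first nintedanib they would hold about 20 + 10 = 30.

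**Baseline against windows.** A switcher's baseline for this period lies at about day 169. That is outside the table's own baseline window (−84 to 1) and inside its 24-week window (128 to 176).

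The stated lengths of the 36- and 52-week windows (84 and 112 days) do not match their limits (309 − 219 + 1 = 91; 407 − 310 + 1 = 98). Allocation follows the start and end days, so nothing above depends on this.

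**The case against.** The case for leaving the text alone has several parts.

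**Columns.** Mixing arises only in the overall column. The default in SAP 7 is randomised group plus total, and SAP 7.8.1 uses the same layout for adverse events in this period. On that reading switchers have their own column, and SAP 5.1 lets a reader work out their time on drug. This stands and limits the point, but the labels in that column remain wrong as time on drug.

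**Liver safety.** A reader might infer that early liver signals in switchers would be diluted or lost. The documents do not support that. SAP 5.4.4 and 7.8.2.2 plan, for the nintedanib exposure period, elevations by threshold, signs of hepatic injury, worst values, time to first elevation with early categories, and individual time courses. None of these is built on the Table 6.7: 1 rows. Nor are frequencies of abnormal values over the whole period.

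**Precision.** One might turn 20 against 30 children into a standard error ratio of √(30/20) = 1.22. The standard summary set in SAP 7 is N, mean, SD, minimum, median and maximum, and laboratory analyses are descriptive, so this ratio describes no planned output. The early values are not lost either; they appear under a later visit.

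**Empty early rows.** It would be too strong to say that switchers never appear there. Unscheduled tests shortly after a day-169 switch can fall in the 24-week window. Under the early-switch option in protocol 3.1, a switch on day 60 would put the two-week value on day 74, in the 12-week row.

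**Choice of clock.** Keeping nominal trial visits can be defended for a descriptive table. It sits badly, however, with a baseline that the SAP has already moved.

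**Conclusion.** The point holds for by-visit laboratory summaries of the nintedanib exposure period. The visit clock contradicts the baseline defined for the same period. In the overall column about a third of the 26-week row reflects about 2 weeks of drug. In columns by randomised group the fault is mislabelling alone.

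It is a minor-to-moderate error in descriptive tables. It touches no primary or secondary endpoint, no period-level abnormality frequency and none of the dedicated liver analyses.

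The conclusion assumes planned numbers, no dropout and a switch at Visit 6. It also assumes that neither the analysis dataset plan nor the sponsor's laboratory standard sets another rule. Neither document is available here, and the SAP text itself gives none.

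**What to change.** State in SAP 6.7, and refer to it from 7.8.2.1, that for by-visit summaries of the nintedanib exposure period day 1 is the first nintedanib intake and the Table 6.7: 1 windows are applied to that day. Keep first trial drug intake as the reference for the double-blind and whole-trial periods. An alternative that removes the mixing but not the mislabelling is to omit the overall column from by-visit displays of this period.

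The cost is one sentence and one derived day variable, with no new data. There are three small downsides:

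- The same sample will carry different visit labels in different period tables.
- Planned switchers will still have no scheduled values in the 6- and 24-week rows, because nintedanib days 15, 85, 197, 281 and 365 miss both windows.
- 28 and 40 weeks on drug will fall in the 26- and 36-week windows, which a table footnote can say.

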7.8.2.2 Liver enzyme and bilirubin elevations

A thorough description of liver enzymes and bilirubin elevations, as defined in [Section 5.4.4](#), will be given for the double-blind period, for the nintedanib exposure period and over the whole trial by treatment group and overall, including:

- Summary table of liver enzyme elevation
- Summary of signs of hepatic injury (see [Section 5.4.4](#))
- Summary table of individual maximum liver enzyme and bilirubin elevations
- Time to first onset and number of patients with liver enzyme elevation. The time to onset of first liver enzyme and bilirubin elevation [days] will be summarized according to both, quartiles from Kaplan-Meier curve
- Kaplan-Meier plot of time to first liver enzyme elevation. No statistical test will be performed. Separate plots will be presented by treatment group.
- Single time course profiles of liver enzymes and other laboratory parameters (ALT, AST, alkaline phosphatase, total bilirubin, absolute eosinophils, eosinophils/leukocytes, GGT) for all patients (maximum individual elevations given in [Section 5.4.4](#)).
- Graphical displays of potential Hy's law cases

7.8.3 Vital signs

Only descriptive statistics are planned for this section of the report.

7.8.4 ECG

Not applicable (ECG findings are reported as adverse events).

9. ADDITIONAL SECTIONS

9.1 PEDSQL SCORING INSTRUCTIONS

The Reports of the PedsQL™ 4.0 Generic Core Scales ([22](#)) for:

- Young Children (ages 5-7),
- Children (ages 8-12),
- Teens (ages 13-18),

and respective parent reports, are composed of 23 items comprising 4 dimensions.

1. On the PedsQL Generic Core Scales, for ease of interpretability, items are reversed scored and linearly transformed to a 0-100 scale, so that higher scores indicate better HRQOL (Health-Related Quality of Life).
2. To reverse score, transform the 0-4 scale items to 0-100 as follows: 0=100, 1=75, 2=50, 3=25, 4=0.
3. To create Scale Scores, the mean is computed as the sum of the items over the number of items answered (this accounts for missing data). If more than 50% of the items in the scale are missing, the Scale Score should not be computed. Imputing the mean of the completed items in a scale when 50% or more are completed is generally the most unbiased and precise method. To do this, count the number of missing values in the scale (call it nmiss). Next, sum the item scores and divide by the number of items in the scale minus nmiss.
4. To create the Psychosocial Health Summary Score, the mean is computed as the sum of the items over the number of items answered in the Emotional, Social, and School Functioning Scales. The Physical Health Summary Score is the same as the Physical Functioning Scale Score.
5. To create the Total Scale Score, the mean is computed as the sum of all the items over the number of items answered on all the Scales.

[figure not shown]
DESCRIPTION OF THE QUESTIONNAIRE:

[figure not shown]
Dimensions	Number of Items	Cluster of Items	Reversed scoring	Direction of Dimensions
Physical Functioning	8	1-8	1-8	Higher scores indicate better HRQOL.
Emotional Functioning	5	1-5	1-5	
Social Functioning	5	1-5	1-5	
School Functioning	5	1-5	1-5	

[figure not shown]
SCORING OF DIMENSIONS:

[figure not shown]
Item Scaling	5-point Likert scale from 0 (Never) to 4 (Almost always) 3-point scale: 0 (Not at all), 2 (Sometimes) and 4 (A lot) for the Young Child (ages 5-7) child report
Weighting of Items	No
Extension of the Scoring Scale	Scores are transformed on a scale from 0 to 100.
Scoring Procedure	
Step 1: Transform Score
 
Items are reversed scored and linearly transformed to a 0-100 scale as follows: 0=100, 1=75, 2=50, 3=25, 4=0.
 
Step 2: Calculate Scores
 
Score by Dimensions:
 
 • If more than 50% of the items in the scale are missing, the scale scores should not be computed, • Mean score = Sum of the items over the number of items answered. 
Psychosocial Health Summary Score = Sum of the items over the number of items answered in the Emotional, Social, and School Functioning Scales.
 
Physical Health Summary Score = Physical Functioning Scale Score
 
Total Score: Sum of all the items over the number of items answered on all the Scales.

Interpretation and Analysis of Missing Data	
If more than 50% of the items in the scale are missing, the Scale Scores should not be computed.
 
If 50% or more items are completed: Impute the mean of the completed items in a scale.

[figure not shown]
Figure 9.1: 1 Description of the PedsQL questionnaire

[figure not shown]

[figure not shown]

[figure not shown]

[figure not shown]

[figure not shown]

[figure not shown]

[figure not shown]

[figure not shown]

[figure not shown]
9.4 LIST OF POTENTIAL TERMS FOR HEPATIC INJURY DERIVATION

[figure not shown]
The table below shows the list of potentially relevant MedDRA preferred terms to support the derivation of a potential hepatic injury.

[figure not shown]
Table 9.4: 1 List of potentially relevant MedDRA preferred terms

[figure not shown]
Symptom	Selection via	MedDRA decode	MedDRA code
Vomiting	Preferred Term	Vomiting	10047700
Fatigue	Preferred Term	Fatigue	10016256
Nausea	Preferred Term	Nausea	10028813
Right upper abdominal quadrant pain or tenderness	High Level Term	Gastrointestinal and abdominal pains (excl oral and throat)	10017926
Fever	Preferred Term	Pyrexia	10037660
Rash	BIcMQ	Skin rash potentially related to drug use (BIcMQ) (narrow)	30000087

[figure not shown]

[figure not shown]

[figure not shown]

[figure not shown]

[figure not shown]

[figure not shown]

[figure not shown]

[figure not shown]

[figure not shown]

[figure not shown]

